#### 6.4.1.2. Secondary Analyses

The clinical cure at Day 21 assessed by an independent adjudication committee based on newly defined clinical cure criteria post hoc will be the secondary analysis. The secondary analysis will be performed based on the micro-ITT and PP Populations in the same manner as the primary analysis.

#### **6.4.2. Secondary Clinical Efficacy Endpoints**

Secondary endpoints will be analyzed using a hierarchical sequential testing procedure in the following predefined order.

1. Proportion of patients with Clinical Cure at Day 28
2. Proportion of patients with Clinical Cure at Day 14
3. All-cause mortality at Day 28
4. Pneumonia-related mortality at Day 28
5. Proportion of patients with Clinical Cure at Day 7
6. Change from baseline in respiratory functional assessment: Time on mechanical ventilation (including if tracheostomy is in place). Time on supplemental oxygenation. Measures of respiratory health such as changes in PaO2/FiO2, using arterial blood gases and/or pulse oximetry measurements.
7. Mean change from baseline in overall clinical status measured by SOFA scores.
8. Health economics: antibiotic utilization, duration of stay in the ICU, duration of hospitalization, duration of intubation with ventilation or duration of mechanical ventilation if tracheostomy is in place.

##### **6.4.2.1. Clinical Cure**

The proportion of subjects with clinical cure at Day 7, Day 14, and Day 28 will be analyzed using stratified CMH test. The P-value will be presented. The number and percentages of subjects with the clinical cure at the different timepoints will be summarized by treatment group for the micro-ITT Population.

Time to clinical cure is defined as the number of days from the administration of the study drug to the date of the first clinical cure assessed by the investigator plus 1.

Time to clinical cure will be evaluated by the Kaplan-Meier method and compared using the stratified log-rank test based on the stratification factors at randomization. The stratified log-rank P-value will be presented. In addition, the Kaplan-Meier estimate of Q1, Q3, and the median time to the event and the associated 95% confidence interval will be presented for each treatment group. Subjects without clinical cure will be censored to the last assessment date.

The number and percentage of subjects with clinical cure and subjects censored will be tabulated by treatment group for the micro-ITT Population.

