9.3 Statistical Methods

Continuous data will be summarized by means, standard deviations, median, min, and max. Categorical data will be summarized by frequency and percentages.

The primary endpoint of Clinical Cure rate at Day 21 will be analyzed using a stratified Cochran-Mantel-Haenszel (CMH) test. The CMH test will be stratified by baseline randomization strata. Time to Clinical Cure will be analyzed using a stratified log rank test. Other continuous endpoints will be analyzed using an Analysis of Covariance (ANCOVA), with treatment as a main effect, site, and baseline strata as covariates. Treatment by site interaction will be evaluated separately. Secondary endpoints will be analyzed using a sequential procedure in predefined order. Categorical variables will be analyzed using a stratified CMH test.

The primary comparisons for all endpoints will be between the 20 mg/kg dose group and placebo and will be done at 0.05 level of significance. The details of the planned analyses will be provided in the Statistical Analysis Plan.

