**Table 2**                    **Criteria for Clinical Cure**

---

1.	The subject must be alive through the index day visit
----	---

---

2.	The patient must have improved respiratory function evaluated at the index day, because: 

• The patient is now off the ventilator and extubated

	or
3.	if the patient entered the study with mechanical ventilation due to reasons other than pneumonia and was assessed " likely ventilated beyond day 28 " at screening, criteria #1 (survival) and #4 (no signs and symptoms of pneumonia) are sufficient to establish Clinical Cure ( presumed not ventilated )

---

4.	The subject must show no clinical signs and symptoms of bacterial pneumonia at the index day, which is determined by 

• Not receiving any antibiotic therapy active against the initial P. aeruginosa strain or against persisting pulmonary bacterial infection for 48 hours (antibiotic therapy for documented extra-pulmonary infection permitted)

	and
	• Resolution of signs and symptoms of bacterial pneumonia, as determined by the PI based on their clinical assessment . Parameters to be considered may include: 

○ Absence of lung abscess or empyema

○ Fever > 38°C or hypothermia (< 35°C) attributable to the primary bacterial pneumonia

○ Tachypnea or shortness of breath (> 22 respirations/min) if off the ventilator and/or back to baseline respiratory rate

---

- 
- Tachycardia (> 100 bpm) or bradycardia (< 60 bpm) and/or back to baseline heart rate
  - Improvement of hypoxemia (ABG or PaO2/FiO2 > 200 or pulse oximetry > 90%)
  - If patient still produces sputum - negative *P. aeruginosa* culture from sputum, blood or pleural fluid
- 

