#### **6.1.3. Hypotheses**

1. Treatment of *P. aeruginosa* pneumonia with Aerucin® improves the rate of Clinical Cure of the index pneumonia.
2. Treatment of *P. aeruginosa* pneumonia with Aerucin® results in an increase in survival rate in the target population
3. Treatment of *P. aeruginosa* pneumonia with Aerucin® improves microbiological, functional and health economic outcomes overall.
4. Aerucin® at the proposed dose level is safe based on clinical observation, standard laboratory tests, and frequency and nature of related adverse events.
5. Aerucin® does not trigger an adverse immunogenic response (i.e., anti-Aerucin® immunogenicity).

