#### **6.1.5. Handling of Dropouts and Missing Data**

Missing data will be handled as follows:

- For clinical outcome at Day 7, 14, 21, and 28, missing data will be handled using the nearest clinical data available prior to that day, i.e. last observation carried forward (LOCF) approach.
- For microbiological outcome at Day 7, 14, 21, and 28, missing data will be handled using the nearest microbiological data available prior to that day, i.e. **LOCF approach**.
- In cases of missing or incomplete dates [e.g. adverse event (AE) and concomitant medications], the missing component(s) will be assumed as the most conservative value possible. For example, AEs with missing start dates, but with stop dates either overlapping into the treatment period or missing, will be counted as treatment-emergent, taking the **worst-case approach**. When partial dates are present in the data, both a partial start date and/or a partial stop date will be evaluated to determine whether it can be conclusively established that the AE started prior to the start of study drug or ended prior to the start of study drug. If the above cannot be conclusively established based on the partial and/or present dates, then the AE will be considered as treatment-emergent. Actual data values will be presented in the data listings.
- A conservative approach will be taken to assess the relationship of an AE to study drug: if the relationship of an event is missing, it will be considered treatment-related. Missing severity for an AE will not be imputed.
- **Missing values for other variables will not be imputed** and only observed values will be used in data analyses and summaries.

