## 6.4. Efficacy Analyses

### 6.4.1. Primary Clinical Efficacy Endpoint

#### 6.4.1.1. Primary Analysis

The primary efficacy endpoint is the **proportion of patients** with clinical cure at Day 21 in patients treated with Aerucin® versus the placebo group as assessed by the investigator. The investigators' assessment will be the primary analysis of the primary endpoint.

The proportion of patients with clinical cure rate at Day 21 will be summarized by randomized treatment based on the micro-ITT Population and will be analyzed using a **stratified Cochran-Mantel-Haenszel (CMH) test** based on baseline randomization strata (stratum 1: VABP or non-VABP, stratum 2: PaO2/FiO2 ≤200 or >200, and stratum 3: Americas, Eastern EU, Western EU and Asia). The **P-value** from the stratified CMH test will be presented. Prior to the unblinding, the assessment of each strata and strata combinations with respect to the sample size and the corresponding number of endpoints if any or some strata need to be combined to be able to process with the analysis or an **alternative method is called for (e.g. Fisher's Exact test).**

For the primary analysis, subjects who dropped out or had missing outcome data will be included in the denominator. Missing data will be imputed using the nearest clinical data available prior to that day, i.e. LOCF approach.

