### **6.4.2.3. Respiratory Functional Assessments and SOFA Scores**

The following respiratory functional assessment endpoints will be summarized by treatment group based on the micro-ITT Population:

- Time on mechanical ventilation (including if tracheostomy is in place);
- Time on supplemental oxygenation; and
- Measures of respiratory health such as changes in PaO2/FiO2, using arterial blood gases and/or pulse oximetry measurements.

Time on mechanical ventilation is defined as the total number of days on mechanical ventilation after the administration of the study drug.

Time on supplemental oxygenation is defined as the total number of days on supplemental oxygenation after the administration of the study drug.

Time on mechanical ventilation and time on supplemental oxygenation will be summarized by treatment group.

PaO2/FiO2 ratio and SOFA score at baseline, post-baseline visits, and change from baseline will be summarized by treatment group based on the micro-ITT Population.

Time on mechanical ventilation, time on supplemental oxygenation, change from baseline in PaO2/FiO2 ratio and SOFA scores will be analyzed using an Analysis of Variance (ANOVA) model, with treatment as a main effect, site and baseline randomization strata as factors. Treatment by site interaction will be evaluated separately. The least squares (LS) mean, standard errors, and the 2-tailed 95% confidence intervals of the change for each treatment group will be estimated. For the between-treatment group comparisons, the differences in LS means, corresponding standard errors, 95% confidence intervals, and p-values will be obtained from the ANOVA model and presented.

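### Time to cure censors subjects who die uncured, so its Kaplan-Meier median and upper quartile can read too early; raw ventilation and oxygen days need a supportive display that accounts for death

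*SAP*

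**What the plan says.** SAP 6.4.2.1 measures time to cure in days from dosing to the first investigator-assessed cure, plus 1. It reports Kaplan-Meier quartiles and a stratified log-rank P-value, and adds: "Subjects without clinical cure will be censored to the last assessment date". Death is not an exception, and Protocol 6.7 lists death among the reasons for early termination. Protocol 9.3 names the test: "Time to Clinical Cure will be analyzed using a stratified log rank test".

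Elsewhere a subject who dies uncured counts against cure. In SAP 6.4.1.1, "subjects who dropped out or had missing outcome data will be included in the denominator". The adjudicated criteria in SAP Table 2 begin with "The subject must be alive through the index day visit".

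For ventilation, SAP 6.4.2.3 says "Time on mechanical ventilation is defined as the total number of days on mechanical ventilation after the administration of the study drug". Oxygen time is defined in the same way, and both are compared by ANOVA without mention of death. The missing-data rules do not mention death either. SAP 6.1.5 says "Missing values for other variables will not be imputed", while Protocol 9.3.5 applies LOCF to missing secondary efficacy data.

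**The concern.** Censoring assumes that the subject could still have been cured later. A subject who has died cannot be. Each uncured death therefore passes its weight to those still at risk, and the curve rises faster than the proportion of treated subjects actually cured. A clinician who reads the median as the day by which half the arm had been cured gets too early a day, and the error is larger in the arm with more uncured deaths.

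The plan itself expects the arms to differ in mortality: its second hypothesis is that treatment "results in an increase in survival rate in the target population". If so, the quartiles flatter placebo more than Aerucin, and the log-rank result moves partly with mortality. The SAP does not say which question that test is meant to answer.

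Raw ventilation and oxygen days have a related but smaller problem: an early death counts as a short duration and a late death as a long one.

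**Working it through.** **Inputs.** Cure of 65% on placebo and 85% on Aerucin, and 77 per arm, come from SAP 4. Follow-up is 28 days. The plan gives no power or expected quartile for time to cure, so there is no plan figure to reproduce, and it gives no planning mortality. The following are therefore assumptions: 20% (placebo) and 10% (Aerucin) die uncured, deaths are spread evenly over Days 2-19, 2-27 or 10-27, and cures evenly over Days 5-21 or 5-28. Uncured survivors are censored at Day 28. Days are study days; add 1 for the SAP scale.

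**Formula.** Per 100 subjects, with c_t cures on day t and n_t still at risk, Kaplan-Meier gives 1 − Π(1 − c_t/n_t). The true proportion cured is Σc_t/100.

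**One median by hand (placebo, cures Days 5-21, deaths Days 2-19).** There are 65/17 = 3.82 cures and 20/18 = 1.11 deaths per day.
- By the start of Day 16 there have been 11 × 3.82 = 42.1 cures and 14 × 1.11 = 15.6 deaths, so 100 − 42.1 − 15.6 = 42.4 are at risk (unrounded inputs).
- The curve stood at 46.9% after Day 15. After Day 16 it is 1 − 0.531 × (1 − 3.82/42.4) = 51.7%, so the median reads Day 16.
- The true proportion cured is 12 × 3.82 = 45.9% on Day 16, 49.7% on Day 17 and 53.5% on Day 18, so the true median is Day 18.

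**All placebo cases, Kaplan-Meier against true:**

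| Cures | Deaths | Median | Upper quartile |
|---|---|---|---|
| Days 5-21 | Days 2-19 | 16 v 18 | 21 v not reached |
| Days 5-21 | Days 2-27 | 17 v 18 | not reached in either |
| Days 5-21 | Days 10-27 | 17 v 18 | not reached in either |
| Days 5-28 | Days 2-19 | 20 v 23 | 27 v not reached |
| Days 5-28 | Days 2-27 | 21 v 23 | 28 v not reached |
| Days 5-28 | Days 10-27 | 22 v 23 | 28 v not reached |

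The true upper quartile is never reached because only 65% are cured. The lower quartile stays at Day 11 in the first three rows. In the fourth it reads Day 13 instead of 14: the curve is at 26.6% on Day 13, and the truth is 9 × 65/24 = 24.4%. On Aerucin with cures on Days 5-21, only the upper quartile moves, from 19 to 18, and only with the earliest deaths.

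**Check with constant hazards (65% cured and 20% dead uncured by Day 21).** The total hazard is −ln(0.15)/21 = 0.0903 and the cure hazard is 0.0903 × 65/85 = 0.0691. The Kaplan-Meier median is ln 2/0.0691 = 10.0 days. The true median is −ln(1 − 0.5 × 85/65)/0.0903 = 11.7 days.

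**Log-rank power (simulated, 77 per arm, unstratified, cures Days 5-21, the three death timings in order):**
- 20% v 10% mortality: 62/67/71% with deaths censored, 75-77% with deaths kept at risk as not cured.
- 15% v 10%: 76-77% under either rule.
- 10% in both arms: 87/83/80% censored, 75-76% kept at risk.

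Stratifying on all 16 cells generally lowered both rules by about 10 points.

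**Raw ventilation days.** With no effect on weaning, the shift (lower-mortality minus higher-mortality arm) is (difference in mortality) × (mean days in survivors − mean day of death). Assume 14 days in survivors and 30% v 20% mortality. Deaths on Day 7 give 0.10 × 7 = +0.7 day; deaths on Day 20 give 0.10 × (−6) = −0.6. With deaths spread over a range of days and 33% v 20% mortality, simulated shifts ran from about +0.8 to −0.9. Putting every death on Day 5 gives 0.13 × 9 = 1.2. Ventilator-free days with death scored 0 favour the lower-mortality arm whatever the day of death: at 30% v 20%, 0.80 × 14 − 0.70 × 14 = +1.4.

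**The case against.** **The effect is small.** At 20% v 10% mortality with cures on Days 5-21, the placebo median moves 1 to 2 days. Its simulated central 95% sampling range at 77 per arm (deaths Days 2-27) is Days 14-19, which is wider than the bias. The SAP also tabulates the crude number cured, cure at fixed days and mortality at four times. This stands and limits the weight, but none of it corrects the quartiles.

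**A reader might infer that the log-rank test is invalid or has inflated error.** With 65% cure in both arms and 20% v 10% mortality, it favours placebo significantly in 11/7/5% of simulated trials, against a nominal 2.5%. That is not false-positive error. In those trials the cause-specific cure hazards really differ, so the test's own null hypothesis is false. The documents support only that the test answers a different question from the probability of having been cured by a given day.

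**A reader might infer that keeping deaths at risk aligns the endpoint with Table 2.** It does not. Table 2 governs the adjudicated analysis, and a subject cured on Day 10 who dies on Day 15 remains a cure here under either rule.

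**A reader might infer that raw durations are biased against Aerucin.** The sign depends on when deaths occur, and the day count is defined for those who die. The SAP also says "Secondary endpoints will be analyzed using a hierarchical sequential testing procedure in the following predefined order", and both mortality tests precede the durations. The durations are thus formally tested only once mortality has been shown to differ. That is also when the shift arises, so a supportive display is useful, but replacing the endpoint is not justified.

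**Conclusion.** The point holds for the quartiles. SAP 6.4.2.1 sets a definite rule, and that rule can make the median and upper quartile too early whenever uncured deaths are followed by later cures in the same arm. In the cases above the placebo median is 1 to 3 days early, and an upper quartile that is never reached can be reported as reached.

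The existence of the bias follows from the text. Its size rests on assumed mortality, death timing and cure timing. Protocol 1.1 cites pneumonia-attributed mortality of 20% to 33%, but Protocol 4.2 excludes moribund patients, so the trial's rate may be lower.

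The log-rank test is valid as a test of cause-specific cure hazards; what is missing is a statement of the question. The ventilation and oxygen issue is minor, with shifts under one day in either direction when deaths are spread over time.

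The primary endpoint is untouched. Time to cure is a named secondary objective but is not in the ordered testing list. The change is worth making before unblinding because it is cheap, not because the trial's conclusion depends on it.

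**What to change.** **Time to cure (SAP 6.4.2.1).**
- Keep subjects who die before any cure in the risk set as not cured, and censor them at one common time later than the last cure that could be recorded. Day 28 is too early: on the plus-1 scale a Day 28 cure has time 29. The end-of-study window of ±2 days allows time 31, and the follow-up call up to 7 days later allows 28 + 7 + 1 = 36.
- Subjects alive without cure stay censored at the last assessment.
- State the question: first investigator-assessed cure by each day, with death before cure counted as not cured. A death after cure does not reverse the cure.
- Keep the stratified log-rank test and the quartiles, and report the present rule as a sensitivity analysis.

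**Durations (SAP 6.4.2.3).** Leave raw ventilation and oxygen days in the testing order with the planned model. Show them by survival status. Add ventilator-free days to Day 28, with death scored 0, as a supportive analysis outside the order.

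**Missing data.** Reconcile Protocol 9.3.5 with SAP 6.1.5 for secondary endpoints.

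**Cost.** SAP wording and programming before unblinding; the protocol's test and the testing order do not change. With equal mortality the log-rank test loses power (about 75% against 80-87% at 10% mortality), so the reason for the change is the question asked, not power. Ventilator-free days mix survival with duration. Survivors ventilated past Day 28 for reasons other than pneumonia would also score 0 and should be shown separately. Protocol 6.5 requires daily respiratory data only until the pneumonia resolves, so re-intubation between later visits may be missed.

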##### **6.4.2.2. Mortality**

All-cause mortality and pneumonia-related mortality rate by Day 7, 14, 21, and 28 will be tabulated by treatment group for the micro-ITT Population and analyzed using a stratified CMH test based on the stratification factors at randomization. The P-value from the stratified CMH test will be presented. In addition, plots of the Kaplan-Meier estimate of the survival distribution function over time will be presented by treatment group.

### **6.4.2.3. Respiratory Functional Assessments and SOFA Scores**

The following respiratory functional assessment endpoints will be summarized by treatment group based on the micro-ITT Population:

- Time on mechanical ventilation (including if tracheostomy is in place);
- Time on supplemental oxygenation; and
- Measures of respiratory health such as changes in PaO2/FiO2, using arterial blood gases and/or pulse oximetry measurements.

Time on mechanical ventilation is defined as the total number of days on mechanical ventilation after the administration of the study drug.

Time on supplemental oxygenation is defined as the total number of days on supplemental oxygenation after the administration of the study drug.

Time on mechanical ventilation and time on supplemental oxygenation will be summarized by treatment group.

PaO2/FiO2 ratio and SOFA score at baseline, post-baseline visits, and change from baseline will be summarized by treatment group based on the micro-ITT Population.

Time on mechanical ventilation, time on supplemental oxygenation, change from baseline in PaO2/FiO2 ratio and SOFA scores will be analyzed using an Analysis of Variance (ANOVA) model, with treatment as a main effect, site and baseline randomization strata as factors. Treatment by site interaction will be evaluated separately. The least squares (LS) mean, standard errors, and the 2-tailed 95% confidence intervals of the change for each treatment group will be estimated. For the between-treatment group comparisons, the differences in LS means, corresponding standard errors, 95% confidence intervals, and p-values will be obtained from the ANOVA model and presented.

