9.3.5 Missing data

Assessing microbiological outcome at Day 7, 14, 21 (Primary Efficacy endpoint), and 28 will be done using the nearest microbiological data available prior to that day (last observation carried forward, LOCF).

Missing data for secondary efficacy endpoints will be analyzed using the LOCF approach.

For the purpose of sensitivity analysis, missing data will be imputed using baseline observation carried forward (BOCF) and observed case.

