
 
1. To be performed if medically necessary. Follow-up airway specimens to be obtained as medically necessary and prior to extubation and at Day 28 (if not extubated prior to then) for quantitative or semi-quantitative culture.
 
2. SOFA and respiratory data to be collected on Day 0, 12 hours after treatment initiation and on Day 4, 7, 14, 21, 28 while intubated and mechanically ventilated. Parameters for SOFA score calculation should not be older than 72 hours.
 
3. ADA only at screening / baseline and Day 28, or at early termination.
 
4. Pre-dose PK sample to be obtained prior to treatment initiation.
 
5. PK samples to be obtained for the FULL PK sub-study at the following times after initiation of treatment: 2 hours (end of infusion), 4h, 12h, and 24 hours and 1 sample at each of the following visits: Day 4, 7, 14, 21, and 28.
 
6. PK samples for the SPARSE PK sub-study at the following times after initiation of treatment: 1 sample at 2 hours (end of infusion), 1 sample at either 4h, 12h, or 24 hours post-treatment initiation (inclusive) and 1 sample at any of the following visits: Day 4, 7, 14, 21, or 28.
 
7. Eligible subjects are randomized on Day -1, Treatment day is Day 0 for the purpose of monitoring and collecting the required samples over the first 24 hours.
 
8. Clinical Cure will be assessed at Day 7, 14, 21, 28 for the analytical purposes.
 
9. Discharge data to be obtained when discharge occurs or Day 28, whichever occurs first.
 
10. Patients with pneumonia who are intubated are eligible for screening regardless of the type of pneumonia, which will be recorded at the time of screening for all study subjects.
 
11. Vital signs will be recorded at baseline prior to treatment (time 0) and then at 1, 2, 4, 12, and 24 hours post treatment. Vital signs will also be recorded daily thereafter.
 
12. In addition to the screening timepoint, chest x-ray(s) are to be taken at any time as medically indicated.
 
13. Women of child bearing potential must take a urine or serum pregnancy test at the time of Screening.
 
14. For subjects with early discharge, effort must be made to perform all protocol defined procedures outlined for End of Study/Early Termination.
 
15. Subjects who decide to discontinue study assessments prior to Day 28 will receive a study exit safety follow-up phone call on key days (Day 4, 7, 14, 21, 28) until Day 28 (+7 days) to assess Clinical Cure, survival and the status of any adverse events.
 
16. Changes in PaO2/FiO2 ratio (e.g. by arterial blood gases), if available and whenever possible OR changes in non-invasive measures of oxygenation (e.g. by pulse oximetry)
 
17. A few days before or after the specified date is acceptable (<math>\pm 2</math> days)
 
					

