### **6.4.2.4. Health Economics Assessments**

The following health economics endpoints will be summarized by treatment group for the micro-ITT Population:

- Duration of antibiotic utilization;
- Duration of stay in the ICU; and
- Duration of hospitalization.

Duration of antibiotic utilization is defined as the number of days that the subjects received antibiotic therapy after the administration of the study drug.

Duration of stay in the ICU is defined as the total number of days of ICU stay after the administration of the study drug.

Duration of hospitalization is defined as the total number of days of hospitalization after the administration of the study drug.

Duration of antibiotic utilization, duration of stay in the ICU, and duration of hospitalization will be analyzed using an ANOVA model, with treatment as a main effect, site and baseline

randomization strata as factors. The treatment differences in LS means, corresponding standard errors, 95% confidence intervals, and p-values will be obtained from the ANOVA model and presented.

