### **7. PROGRAMMING SPECIFICATIONS**

Analyses will be performed using SAS® version 9.3 or higher. All available data will be presented in subject data listings which will be sorted by subject as applicable. Detailed Programming Specifications will be provided in a separate document.

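### Site is a model factor for the continuous secondary endpoints with no pooling or random-effect rule (about 120 sites, 154 subjects), which probably costs precision, and the change-score models omit the baseline value

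*SAP*

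**What the plan says.** SAP 6.4.2.3 covers time on ventilation, time on supplemental oxygen, and change in PaO2/FiO2 and SOFA. Its ANOVA is specified "with treatment as a main effect, site and baseline randomization strata as factors. Treatment by site interaction will be evaluated separately". It also promises arm-level results: "The least squares (LS) mean, standard errors, and the 2-tailed 95% confidence intervals of the change for each treatment group will be estimated".

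SAP 6.4.2.4 covers the antibiotic, ICU and hospital durations, which "will be analyzed using an ANOVA model, with treatment as a main effect, site and baseline" strata. It promises between-arm results only: "The treatment differences in LS means, corresponding standard errors, 95% confidence intervals, and p-values will be obtained from the ANOVA model".

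Protocol 9.3 and the synopsis also name site and the baseline strata, under the label ANCOVA. Neither document lists the baseline value of the endpoint as a covariate.

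The Sites line of the protocol synopsis gives about 120 sites. SAP 4 gives 154 subjects. SAP 3.1 expects low recruitment at many sites. SAP 3.2 stratifies randomization by VABP status, PaO2/FiO2 and region, in blocks of 4, with no blocking by site. The only combining rule in the SAP (6.4.1.1) concerns the randomization strata in the primary CMH test. On programming, SAP 7 says "Detailed Programming Specifications will be provided in a separate document".

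**The concern.** A factor in an ANOVA is normally fitted as a fixed effect, so the treatment effect is estimated from within-site comparisons. With 154 subjects over as many as 120 sites, an average of 154/120 = 1.3 per site, many sites will have one subject or only one arm. Those subjects contribute almost nothing to the comparison, and each site also uses a degree of freedom.

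At stake is the width of the intervals for steps 6 to 8 of the hierarchy in SAP 6.4.2. Confirmatory testing may stop before these steps, but SAP 6.4.2.3 and 6.4.2.4 present their estimates, intervals and p-values without making that depend on the hierarchy.

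Two features add to this. Treatment-by-site interaction can be estimated only in sites that contain both arms. The change-score models for SOFA and PaO2/FiO2 leave out a baseline value that is already collected.

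**Working it through.** **The plan's own figures.** 69/(1 - 0.10) = 76.7, so 77 per group and 154 in total, which reproduces SAP 4. The plan states no power or precision for the continuous endpoints, so there is no such figure to reproduce.

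**Measure.** Regress the treatment indicator on the strata (residual sum of squares RSS0) and on strata plus site (RSS1). At ICC 0 the treatment information retained is R = RSS1/RSS0.

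**Hand check, limiting case.** Suppose all 120 sites enrol and as evenly as possible. Then 154 - 120 = 34 sites have two subjects and 86 have one. About half of the pairs, 17 to 18 sites (about 35 subjects), contain both arms. Each such pair contributes 2 x 0.5^2 = 0.5, so RSS1 is about 17.5 x 0.5 = 8.75. RSS0 is about 154 x 0.25 = 38.5. R is about 8.75/38.5 = 0.23, and the simulated value is 0.22. This is an extreme, not the expected case.

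**Simulated accrual.** Assumptions: N = 154, blocks of 4 in 2 x 2 x 4 cells, 70% VABP, 50% with PaO2/FiO2 at or below 200, sites split evenly over four regions. Subjects fall on open sites equally or by gamma weights, where a smaller shape means more uneven accrual. Retained information R:

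| Open sites | Equal | Shape 2 | Shape 1 | Shape 0.5 | Shape 0.3 |
|---|---|---|---|---|---|
| 120 | 0.44 | 0.51 | 0.56 | 0.64 | 0.71 |
| 60 | 0.65 | 0.70 | 0.73 | 0.78 | 0.83 |
| 40 | 0.77 | 0.79 | 0.81 | 0.85 | 0.88 |
| 20 | 0.89 | 0.90 | 0.91 | 0.92 | 0.94 |

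At 120 open sites, 47 to 86 enrol anyone and only about 23 to 28 have both arms. The loss at ICC 0 is 1 - R. A repeat simulation moved the ends by about one point, and the ranges below take the wider ends.

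**Allowing for between-site variance.** At ICC rho and total variance 1, with T_s the sum of the treatment residuals in site s:

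- Without site: V0 = [(1 - rho) RSS0 + rho x sum of T_s^2] / RSS0^2
- With fixed site: V1 = (1 - rho) / RSS1
- Net loss = 1 - V0/V1; break-even is the rho at which V0 = V1

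If the sum of T_s^2 is close to RSS0, net loss is about 1 - R/(1 - rho) and break-even is about 1 - R. For 120 sites and equal accrual: 1 - 0.44/0.90 = 0.51 and 1 - 0.44 = 0.56, against simulated 51% and 0.57. Under uneven accrual the sum is smaller, which raises both results.

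| Open sites | Loss, ICC 0 | Net loss, ICC 0.10 | Break-even ICC |
|---|---|---|---|
| 120 | 29-56% | 23-51% | 0.33-0.57 |
| 60 | 17-36% | 11-29% | 0.24-0.37 |
| 40 | 12-24% | 6-17% | 0.18-0.26 |
| 20 | 6-11% | 1-3% | 0.13-0.15 |

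**What a random site effect recovers.** At ICC 0.10 (taken as known), with 120 planned sites and somewhat different assumed regional and stratum splits, the standard error in SD units is 0.159 to 0.161 with random site. It is 0.188 to 0.329 with fixed site; the upper value is the case in which all 120 enrol.

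**Omitted baseline value.** For change in SOFA, with r the baseline to follow-up correlation and k = baseline SD / follow-up SD, adding the baseline cuts the residual variance by (r - k)^2 / (1 + k^2 - 2rk). At k = 1 and r = 0.5 this is 0.25/1 = 25%.

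| k | r = 0.3 | r = 0.5 | r = 0.7 |
|---|---|---|---|
| 1 | 35% | 25% | 15% |
| 0.8 | 22% | 11% | 2% |
| 0.6 | 9% | 1% | 2% |

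For PaO2/FiO2 the stratum already adjusts in part. The simulated gains at the same r are 16-19%, 11-12% and 6-7% (k = 1), 9-10%, 4-5% and 1% (k = 0.8), and about 4%, 1% and 1% (k = 0.6). Neither r nor k is given.

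**The case against.** Adjusting for site is a legitimate choice. Antibiotics follow each institution's practice, so outcomes may differ between sites. If the ICC is above break-even, or few sites enrol, the fixed-site model is as precise or better: at 20 sites and ICC 0.20 it is about 5-7% better. The protocol names site, no power is claimed for these endpoints, and steps 6 to 8 may never be tested confirmatorily. All of this stands. It limits the size of the point but does not remove it, because the SAP has no rule for the sparse case that it expects.

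Three stronger readings are tempting, and the documents do not support them.

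- *The arm-level LS means cannot be estimated.* Region is determined by site. With site and region crossed and equally weighted, these means were estimable in only 0, 3 and 34 of 240 simulated designs at 120, 60 and 40 sites. But the SAP does not specify that coding and leaves programming to another document. With sites nested in region they were estimable in every design checked, and with observed-margin weights in 240 of 240. Treatment differences are always estimable, and SAP 6.4.2.4 promises only those.
- *SOFA data will be far sparser, so the loss is larger there.* SAP Table 1, note 2, schedules follow-up SOFA "on Day 4, 7, 14, 21, 28 while intubated and mechanically ventilated", and SAP 6.1.5 says that for variables outside its imputation rules "only observed values will be used in data analyses and summaries". But protocol 6.5 also covers the ICU stay, and protocol 9.3.5 says "Missing data for secondary efficacy endpoints will be analyzed using the LOCF approach". Figures for SOFA attrition would rest on one reading of passages that must first be reconciled.
- *The SAP contradicts the protocol by dropping the baseline covariate.* Protocol 9.3 says ANCOVA but does not name the baseline value. Adding it is an improvement; ANCOVA versus ANOVA is a label to align.

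**Conclusion.** The point holds as one of precision. If 60 to 120 sites open and the ICC is about 0.10 or less, the fixed-site model probably discards between about a tenth and a half of the treatment information on the continuous secondary endpoints. At 40 sites the loss is moderate, and at 20 it is slight or reversed. These figures rest on assumed accrual shapes, stratum proportions and ICC. The documents support only the planned number of sites, the sample size, the expectation of small sites and the absence of site stratification.

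A reader might infer bias, an inflated Type I error or a threat to the primary result. None follows: the loss is in variance, and the primary CMH test has no site term. The baseline-covariate gain ranges from about 1% to 35% and may be small if the baseline SD is well below the follow-up SD. The LS-mean weighting is a minor clarification. This is a change that should be made, with medium confidence in its size.

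**What to change.** Before unblinding, amend the SAP:

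1. In 6.4.2.3 and 6.4.2.4, fit site as a random effect, or pool small sites within region by a rule fixed before unblinding. Either keeps the site term of protocol 9.3. A model with the randomization strata alone can be a sensitivity analysis, or the main model if the departure from protocol 9.3 is stated.
2. For change in SOFA and change in PaO2/FiO2, add the continuous baseline value as a covariate.
3. In 6.4.2.3, replace treatment-by-site with treatment-by-region interaction, and record this as a departure from protocol 9.3.
4. Minor: if site stays fixed, state the LS-mean weights (sites nested in region, or observed margins).
5. Reconcile SAP Table 1, note 2, with protocol 6.5, and SAP 6.1.5 with protocol 9.3.5, so that the SOFA analysis set is defined. Align the ANCOVA/ANOVA label.

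The cost is SAP wording, with no new data. Protocol 9.3 leaves analysis details to the SAP; any change to its own wording or the synopsis goes through the amendment process in protocol 12.1. The baseline covariate costs one degree of freedom and no subjects, because a change score already needs the baseline. The downside of a strata-only main model is that site differences are absorbed only at region level, and above the break-even ICC fixed site would have been more precise.
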